5.0 Ocular Microbiome Protocol (NAU [name]/[name] Lab)

Microbiome samples from meibomian gland expressed material were collected in the office under strict aseptic precautions in the ophthalmology clinic using sterile gloves and instrumentation. Material was collected and transferred to sterile swab for right eye and left eye samples (COPAN LQ Stuart Transport Swab, COPAN Italia S.p.A, Brescia, Italy). Any contaminated swabs were discarded and repeat sampling performed. After collection, the swab tips were cut with sterilized scissors and placed into Eppendorf tubes and placed in dry ice container. The samples were immediately sent for freezing frozen in a -90°C bath of Novec engineered fluid (3M HFE-7000) cooled in a HistoChill freezing bath (SP Scientific HC80A0). The time from the start of harvest to freezing was approximately 10 -15 minutes. No saline, embedding medium or preservative was added. Unique identification numbers were assigned to each individual container with bar code labels. Biospecimens were stored in ThermoFisher Ultra Low Temp upright freezers at -80°C until shipped to [name]/[name] lab at NAU on dry ice and then stored at -80°C until ready for analysis.

DNA Extraction

Total genomic DNA was extracted using the QIAamp DNA Mini Kit (Qiagen; 51304) with some prior modifications. Briefly, swab heads were placed in sterile 2mL microcentrifuge tubes with 400uL of lysis buffer (20mM Tris-HCI [pH 8.0], 2mM EDTA, 1.2% Triton X-100) containing 1mg/mL Lysozyme (Sigma-Aldrich; L7773), 30U/mL Lysostaphin (Sigma-Aldrich; L2898) and 375U/mL Mutanolysin (Sigma-Aldrich; M4782). Specimens were incubated at 37°C for 1 hour and both the lysates and the swabs were transferred to bead-beating tubes containing 373mg of 0.1mm-diameter zirconia/silica beads (Biospec; 11079101z). Bead-beating was performed at 2100 rpm for 1 min using a Digital Vortex Mixer (Fisher Scientific; 0215370) with a vortex adapter (Mo-Bio; 1300-V1-24). The samples were centrifuged at 12,000xg for 5 minutes and the supernatant was transferred to sterile 1.7mL microcentrifuge tubes. Then, 20uL Proteinase K (20mg/mL) and 400uL Buffer AL were added to each sample and incubated at 56°C for 30 minutes. Further DNA purification was performed as described by the manufacturer.

Library Preparation

16S primers that encompass the V3 and V4 region were selected as the region for library preparation¹⁸. The primer pair, S-D-Bact-0341-b-S-17 and S-D-Bact-0785-a-A-21, corresponds to a region of 16S that on average spans 459 base pairs. The primers were constructed with universal tail (UT) sequences ¹⁹. We modified the protocol from a single index to a dual index approach. Briefly, the common Illumina PCR primer was replaced with a primer containing a second index sequence. Each UT1 and UT2 index was used only once, the advantage of which will be addressed in the discussion. Preparing libraries with universal tails is a 2-step process: target specific amplification and an extension PCR to add the barcodes and Illumina adapter sequences. The target specific primers, in this case 16S primers with universal tails, can be found in Table 1. The target specific amplification in a 25 µl reaction contained 12.5 μl Q5 Hot Start High-Fidelity 2X Master Mix (New England Biolabs Inc.), 1.25 μl of each primer at a stock concentration of 10 μ M (final concentration: 500 nM/primer), and 10 μ l of DNA with the following PCR conditions: 1. Initial denaturation at 95°C for 3 min; 2. 25 cycles of 95°C for 40 sec, 55°C for 2 min, 72°C for 60 sec; 3. Final extension at 72°C for 7 min. The target specific amplicon was purified with Agencourt AMPure XP beads (Beckman Coulter) according to the manufacturer's protocol at a 1:1 ratio based on volume. The DNA was eluted from the beads in 25 µl of 10mM Tris-HCl + 0.05% Tween 20 solution.

The indexing PCR contained 12.5 μ I KAPA HiFi HotStart ReadyMix (KAPA biosystems), 1 μ I each of barcoded UT1 and UT2 indexing primers at stock concentrations of 10 μ M (final: 400 nM/primer) and 10.5 μ I of template from target specific PCR at a final volume of 25 μ I. The PCR conditions were: 1. Initial denaturation at 98°C for 2 min; 2. 6 cycles of 98°C for 30 sec, 65°C for 20 sec, 72°C for 30 sec; 3. Final extension at 72°C for 5 min. The final product was purified with Agencourt AMPure XP beads as previously described above and the DNA was eluted in 35 μ I of Tris-HCI 0.05% Tween 20 solution. The indexed libraries were electrophoresed on a 2% agarose gel at 100V for 1 hour to separate the human mitochondrial 16S (~450 bp) libraries from the bacterial 16S libraries. Gel extraction of the bacterial 16S libraries was performed using the QIAquick Gel Extraction Kit (Qiagen; 28704) following the manufacturer's instructions.

Library Quantification and Sequencing

Individually Indexed libraries were quantified using KAPA Library Quantification Kit— Illumina/ABI Prism (KAPA biosystems) qPCR. The samples were pooled at equimolar concentrations to enable efficient multiplexing during the sequencing. The final library pool was quantified using the same method and was used for the individual libraries. The final library pool was mixed with a phiX control library a phiX control library (Illumina; FC-110-3001) at 25% of the total library material, as per Illumina's instructions for amplicon sequencing, and was loaded onto the Illumina MiSeq at 14pM. PhiX provides the base diversity that the Illumina instrument needs for proper calculations. The library pool was sequenced with 300 bp paired end reads using version 3 chemistry (Illumina; MS-102-3003). Custom sequencing primers for the dual indexed UT libraries were added to the appropriate wells in the MiSeq cartridge at a concentration of 0.5 μ M.

Sequence Processing

Paired end reads for each sample were assembled using SeqPrep. The following changes were made to the default SeqPrep settings: "-L 400", "-n 1", "-A

CAAGCAGAAGACGGCATACGAGAT", and "-B AATGATACGGCGACCACCGAGATCTACAC". The merged reads were clustered into operational taxonomic units (OTUs) at 99% by identity against the greengenes database with QIIME (1.9.1) using a previously described protocol (default parameters and tools unless otherwise noted)²¹. Reads that failed to hit the reference sequence collection were retained and clustered *de novo*. Sequences were aligned using PyNAST and taxonomy was assigned using uclust in the QIIME environment.

Sequence and Statistical Analysis

To determine the baseline variability of the bacterial microbiota within an individual, the V3-V4 region of the 16S rRNA gene was sequenced on the Illumina MiSeq. All analyses were performed on an operational taxonomic unit (OTU; number of clusters of similar sequences) table rarefied to 5500 sequences/sample. Alpha-diversity, which is used to assess diversity, evenness, and richness in a community in a single sample, was measured to ascertain differences in the microbiota between IM and MM across the spectrum of CRS disease. Alpha diversity indices studied were: Faith's phylogenetic diversity (measure of biodiversity incorporating phylogenetic difference between species) and Shannon diversity (richness and evenness; "evenness" is a measure of relative abundance of different species that make up the richness in that area)]. A permutational t-test (999 Monte Carlo permutations) was used to determine changes in alpha-diversity (diversity within a sample). Alpha diversity values were projected onto an image of the sinonasal cavity on the MM middle or IM using SitePainter²².

Beta diversity (comparison of samples to each other to measure the distance or dissimilarity between each sample pair) was performed using UniFrac distance matrices generated in QIIME 1.9.0. Average weighted and unweighted UniFrac values were calculated between subjects. Principal Coordinates Analysis (PCoA) plots were used for visualization of the data present in the beta diversity distance matrix using Emperor. Permutational analysis of variance (PERMANOVA) using the adonis function in the R Vegan package was used to determine significance in distance matrices across samples by metadata categories. Procrustes analysis was performed on the first three dimensions of a PCoA generated using a weighted UniFrac distance matrix and a Monte Carlo simulation was performed with 10000 permutations to determine significance. Procrustes sum of squares (m^2) and correlation [$r = \sqrt{(1 - m^2)}$] are reported. To confirm the Procrustes findings, a two-sided Mantel test with 10000 permutations was performed on weighted UniFrac distances matrices generated independently for each sample within a pair.

6.0 Intense Pulsed Light – Meibomian Gland Expression (IPL-MGX) treatment protocol

Subjects undergo Fitzpatrick skin typing to classify their skin response to ultraviolet exposure by degree of burning and tanning. Fitzpatrick skin types I, II, III, and IV are included as recommended by the manufacturer, and V and VI were excluded. Quadra Q4 IPL Machine (**DermaMed Solutions, LLC**, Lenni, Pennsylvania) is used for all subjects. Subjects will have ocular rosacea and will not have active lesions, skin cancer, or specific skin pathology that would exclude treatment with IPL.

Subjects will receive four IPL-MGX treatments, each spaced four to six weeks apart. IPL machine will be set to appropriate dry eye settings—either 1D, 2D, or 4A. At each treatment, the eyelids are bilaterally closed and sealed shut with IPL-Aid disposable eye shields (Honeywell Safety Products, Smithfield, Rhode Island). After generous application of ultrasonic gel to the treated skin, subjects receive approximately 30-40 pulses (with slight overlapping applications) from the right preauricular area, across the cheeks and nose to the left preauricular area, treating up to the inferior boundary of the eye shields. Each treatment is followed by MGX with Hardten expression forceps to empty meibum from bilateral upper and lower eyelids. Expressed material is sent for ocular microbiome testing at NAU. Subjects use tobramycin/dexamethasone drops twice a day for two days following IPL-MGX treatment.

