2.4 Data Collection and Analysis

Appointment 1/Baseline. Data will be collected on the participants first visit ("baseline") and will include the following: OSDI, visual acuity, slit lamp imaging, lissamine green staining, fluorescein, tear film break up time (TBUT), Schirmers 5 minute with anesthesia osmolarity, meibography, Keratograph5 redness evaluation, Lipiview lipid tear film thickness, , tear cytokine evaluation and impression cytology (for flow cytometry of labeled cells for inflammatory markers), and tear sample for ocular microbiome testing.

number identifier, and their data will be entered into an Excel Document ("data file") and RedCap database which will be kept on a secure server at Mayo Clinic Arizona.

[figure not shown]
At appointment 1, participants will receive the initial treatment of either MGX or MGX+IPL. At appointment 1, participants will be given Tobramycin-Dexamethasone ophth soln to use BID topically OU for 2 days, and told to avoid UV exposure for 3 weeks.

Appointment 2. 4-6 weeks after appointment 1, at appointment 2, participants will be evaluated using OSDI, visual acuity, Icare tonometry, slit lamp imaging, lissamine green staining, fluorescein staining. This data will be entered into the data file. Participants will receive their second treatment of either MGX or MGX+IPL. At appointment 2, participants will be given Tobramycin-Dexamethasone ophth soln BID for 2 days, and told to avoid UV exposure for 3 weeks

Appointment 3. 4-6 weeks after appointment 2, at appointment 3, participants will be evaluated using OSDI, visual acuity, Icare tonometry, slit lamp imaging, lissamine green staining, fluorescein staining. This data will be entered into the data file. Participants will receive their second treatment of either MGX or MGX+IPL. At appointment 3, participants will be given Tobramycin-Dexamethasone ophth soln BID for 2 days, and told to avoid UV exposure for 3 weeks

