Impression Cytology. Impression cytology is used to sample conjunctival epithelium which has been shown to be affected in DED. [34, 35] The test is minimally invasive, and is well validated within the literature.[34, 35] Using flow cytometry, the expression of 4 markers: HLA-DR (an inflammatory marker), Fas antigen (CD95), Fas ligand, and APO2-7 (apoptotic markers), will be quantified based on previously published reports.[36] Published studies have shown these markers to be upregulated in DED and therefore a biomarker of ocular surface inflammation. [34, 37] Cost is estimated to be \$4,000 for all samples for the entirety of the study, which includes antibodies, consumables and service charges.

Microbiology Identification. This test is used to examine the changes in microbiological flora of the eye. Conjunctival swabs will be obtained from patients and sent for RNA sequencing. Previous studies have shown ocular surface bacteria to be related to various ocular surface disease.[38] Additionally, the presence of *Demodex* has been shown to influence meibomian gland dysfunction, cause inflammation, and lead to changes in tear cytokine levels such as IL-17[39, 40]. Through this method, we will be able to assess changes in the ocular microbiome, including alterations in *Demodex*, with MGX/IPL versus MGX alone. Cost is estimated to be \$30.07/sample, with a total cost for all 40 samples \$2,500. See Section 5 for detailed protocol.

Pharmacy costs: Acuvail costs total \$10,000. This is due to the need for 8 vials of the preservative free ampules to be given for OU BID dosing after each treatment session, totaling 640 vials.

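### The microbiome specimen is specified three ways, and the expressed-meibum option leaves the IPL arm without a pre-treatment baseline

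*Combined protocol and SAP*

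**What the plan says.** One endpoint has three specimens and two assay descriptions.

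- Section 2.4 lists a "tear sample for ocular microbiome testing" among the evaluations at appointment 1, and uses the same words at appointment 4, ahead of the final treatment.
- Section 3.2 (Microbiology Identification) says: "Conjunctival swabs will be obtained from patients and sent for RNA sequencing". It gives 40 samples, 30.07 dollars per sample and a total of 2,500 dollars, and refers to Section 5 for detail.
- Section 5.0 says: "Microbiome samples from meibomian gland expressed material were collected in the office". The material goes onto separate right-eye and left-eye swabs. The assay starts from DNA ("Total genomic DNA was extracted using the QIAamp DNA Mini Kit") and sequences the V3-V4 region of the 16S gene.
- Sections 6.0 (IPL-MGX) and 7.0 (MGX only) share one sentence: "Expressed material is sent for ocular microbiome testing at NAU".

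The order of steps is stated. In Section 6.0 about 30-40 pulses come first, and then "Each treatment is followed by MGX with Hardten expression forceps". In Section 7.0 expression stands alone. Section 2.4 gives the first treatment at appointment 1, which is the baseline visit. Section 1.4 makes microbiome testing a baseline and end-of-study measure and hypothesises a better result with IPL than with MGX alone. No section describes an expression before IPL.

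**The concern.** Tears, conjunctiva and gland contents are different sites. Staff working from this document cannot tell which to collect, in which eye, at which visits, or whether before or after treatment. Section 3.2 sends them to Section 5.0, which describes another specimen and another starting nucleic acid.

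The choice matters for the comparison between arms. A tear sample or conjunctival swab taken with the other appointment 1 tests precedes treatment in both arms. Expressed material does so in neither strict nor equal fashion: in the IPL arm it can only be obtained, as Section 6.0 is written, after the pulses. The IPL arm then has no pre-treatment microbiome value, and conditions at collection differ by arm. A pre-treatment specimen that was never taken cannot be recovered in the analysis.

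**Working it through.** **Step 1. Timing of the specimen under each option** (arm sizes from Section 2.3; order of steps from 2.4, 6.0 and 7.0)

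| Specimen | Appointment 1, IPL arm | Appointment 1, control arm | Appointment 4, IPL arm |
|---|---|---|---|
| Tear sample (2.4) | before IPL, if taken with the listed tests | before MGX | before the fourth session |
| Conjunctival swab (3.2) | timing not stated; can precede IPL | can precede MGX | can precede the fourth session |
| Expressed material (5.0, 6.0, 7.0) | after IPL, 10 of 10 | no IPL, 0 of 10 exposed | after the fourth session |

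Section 2.4 defends an assessment after three treatments. Material expressed at appointment 4 would follow the fourth IPL session instead.

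**Step 2. What this does to the contrast.** Take a scalar summary such as a diversity index. Let c be the expected change in controls, L the added lasting effect of the first three IPL sessions, and e1 and e4 the immediate effect of IPL on material expressed at appointments 1 and 4. Pre-treatment means are equal in expectation by randomisation. The IPL-minus-control difference in change is then:

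- Both samples before the pulses: (c + L) - c = L.
- Both after: (c + L + e4 - e1) - c = L + (e4 - e1). This equals L if e4 = e1.
- First after, fourth before: (c + L - e1) - c = L - e1.
- Both before, but the specimen changes between visits and shifts the value by dI in the IPL arm and dC in controls: L + (dI - dC). This equals L only if the shift is the same in both arms.

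If both samples follow the pulses and the analysis adjusts for the first sample with within-arm slope k, the adjusted difference is (L + e4) - k x e1. With e1 = e4 = e this is L + (1 - k)e, so the immediate effect does not cancel unless k = 1 or e = 0.

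The documents give no value for e1, e4, k, dI or dC. No size or sign follows. They also do not fix the estimator: Section 2.4 says only that changes will be analysed, and Section 5.0 names a permutational t-test for alpha diversity and PERMANOVA for distances.

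**Step 3. Sample count** (unit price 30.07 dollars, Section 3.2)

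- 40 samples, as stated: 40 x 30.07 = 1,202.80.
- 80 samples (20 patients x 2 visits x 2 eyes, or 20 x 4 treatments): 80 x 30.07 = 2,405.60.
- 160 samples (20 x 4 treatments x 2 eyes): 160 x 30.07 = 4,811.20.
- Stated total: 2,500 / 30.07 = 83.1 samples.

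The stated count, price and total do not agree. The split of 40 into one sample before and one after treatment per patient is given in Section 3.2 for tear cytokines; for the microbiome it would be an inference.

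**The case against.** The strongest reply is that Section 3.2 defers to Section 5.0, and that 5.0, 6.0 and 7.0 agree on expressed material, which is placed on swabs. The other terms may be loose descriptions, and RNA sequencing may be shorthand for sequencing the 16S rRNA gene. If so, both IPL-arm samples follow IPL and a steady immediate effect drops out of the change score. The pulses also cross the cheeks and nose and stop at the lower edge of the shields, with the lids sealed, so an effect on gland contents within minutes could be small.

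Much of this stands. A reader might infer that any immediate IPL effect is simply subtracted from the IPL arm's change. The documents do not support that, because under the same option the appointment 4 specimen also follows IPL. A reader might also infer that sites are in fact mixed between visits or arms. No section says so: 2.4 uses the same words at both appointments, and 6.0 and 7.0 use the same sentence.

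Two things remain. First, the deferral does not remove the contradiction: the visit schedule in 2.4 still calls for tears, before the final treatment. Second, cancellation needs an additive effect that is alike at sessions 1 and 4, and an unadjusted change score. It does not carry over directly to the between-sample distances analysed in Section 5.0.

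**Conclusion.** The contradiction in specimen and assay is certain on the text. The lack of a pre-treatment baseline in the IPL arm is conditional on using expressed material; given that, it affects all 10 IPL patients and none of the 10 controls. That ratio describes exposure at collection and should not be read as an amount of bias. Bias in the between-arm contrast needs one further condition from Step 2: different timing, a specimen shift that differs between arms, different session effects, or use of the first sample as a true baseline or covariate. Its size and direction are unknown. The endpoint is one of many in a 20-patient pilot. It should be corrected before sampling starts because the loss is irreversible and the correction is cheap.

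**What to change.** - Reconcile Sections 2.4, 3.2, 5.0, 6.0 and 7.0 to one primary specimen and one assay, settling RNA against DNA/16S.
- In both arms, collect the primary specimen at appointments 1 and 4 before any IPL pulse and before expression. The tear sample or the conjunctival swab already in the plan allows this, and the order of treatment steps is untouched.
- If expressed meibum is also kept, report it separately, label it post-IPL in the treated arm, and do not call its first sample a baseline.
- State the eyes, the visits and the number of samples per patient, and correct the count or the cost in Section 3.2.

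The cost is mainly protocol wording and the order of collection within a visit. Expressed meibum becomes a secondary set without a pre-treatment value. Keeping it beside the primary specimen adds sequencing: one extra sample per patient at two visits is 20 x 2 x 30.07 = 1,202.80 dollars at the stated price, and more if both eyes or all four treatments are sampled.

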7.0 MGX only protocol

Subjects undergo Fitzpatrick skin typing to classify their skin response to ultraviolet exposure by degree of burning and tanning. Fitzpatrick skin types I, II, III, and IV are included. Subjects will have ocular rosacea and will not have active lesions, skin cancer, or specific skin pathology that would exclude treatment with IPL (to ensure case controls for test group).

Subjects will receive four MGX treatments, each spaced four to six weeks apart. Each treatment consists of MGX with Hardten expression forceps to empty meibum from bilateral upper and lower eyelids. Expressed material is sent for ocular microbiome testing at NAU. Subjects use tobramycin/dexamethasone drops twice a day for two days following MGX treatment.

References

- 1. McGinnigle, S., S.A. Naroo, and F. Eperjesi, *Evaluation of dry eye.* Surv Ophthalmol, 2012. **57**(4): p. 293-316.
- 2. The definition and classification of dry eye disease: report of the Definition and Classification Subcommittee of the International Dry Eye Workshop. Ocular Surface, 2007. **5**: p. 75-92.
- 3. Labbe, A., F. Brignole-Baudouin, and C. Baudouin, *[Ocular surface investigations in dry eye].* J Fr Ophtalmol, 2007. **30**(1): p. 76-97.
- 4. Nelson, J.D., et al., *The international workshop on meibomian gland dysfunction: report of the definition and classification subcommittee.* Invest Ophthalmol Vis Sci, 2011. **52**(4): p. 1930-7.
- 5. Nichols, K.K., et al., *The international workshop on meibomian gland dysfunction: executive summary.* Invest Ophthalmol Vis Sci, 2011. **52**(4): p. 1922-9.
- 6. Bron, A.J., L. Benjamin, and G.R. Snibson, *Meibomian gland disease. Classification and grading of lid changes.* Eye (Lond), 1991. **5 (Pt 4)**: p. 395-411.
- 7. Chew, C.K., et al., *An instrument for quantifying meibomian lipid on the lid margin: the Meibometer.* Curr Eye Res, 1993. **12**(3): p. 247-54.
- 8. Buchholz, P., et al., *Utility assessment to measure the impact of dry eye disease.* Ocul Surf, 2006. **4**(3): p. 155-61.
- 9. Schiffman, R.M., et al., *Utility assessment among patients with dry eye disease.* Ophthalmology, 2003. **110**(7): p. 1412-9.
- 10. SR, G., *Meibomian glands in chronic blepharoconjunctivitis*. Am J Ophthalmol 1921. **4**: p. 489-494.
- 11. Korb, D.R. and J.V. Greiner, *Increase in tear film lipid layer thickness following treatment of meibomian gland dysfunction.* Adv Exp Med Biol, 1994. **350**: p. 293-8.
